Title of Study:

Development and Evaluation of an Electronic health Record-based Medication Complete Communication (EMC²) Strategy: A Pragmatic, Physician Randomized Trial

Rationale:

There is a well-documented need for effective interventions that can help patients understand and safely adhere to prescribed medications, particularly those with greater potential for harm if not taken correctly. We will leverage health and consumer technologies with our **EHR-based Medication Complete Communication (EMC²) Strategy** to: 1) inform patients about medication risks and safe use, 2) promote provider education and counseling about prescribed drugs and 3) monitor patient adherence outside of visits. The EMC² Strategy could be feasible, sustainable, and readily available to ambulatory care practices.

Objective(s)/Endpoints:

Objectives	Endpoints
Primary • Test the effectiveness of the EMC ² Strategy, compared to usual care on improvement in patient knowledge of prescribed medications	Medication-specific knowledge measured by demonstrated proper understanding of indication, risks and benefits, and side effects at 3 months.
Secondary • Test the effectiveness of the EMC ² Strategy, compared to usual care on improvement in safe use and adherence to prescribed medications	Medication adherence measured by fill, time to fill, demonstrated proper use, and the ASK-12. at 3 months
Tertiary/Exploratory • Evaluate the fidelity of the EMC ² Strategy	 Patient report of provider counseling Patient report of receipt of print Rx information Completion of EHR portal survey Clinic follow-up (yes or no) for patients identifying Rx concerns via portal survey

Summary of Pragmatic Study Design:

Study B3D-US-B029 (STU00207507) is a 2-arm, multi-site, physician-randomized pragmatic trial to evaluate the impact and scalability of the Phase I EMC^2 strategy to promote safe medication use and adherence.

Treatment Arms and Duration:

Usual Care. Usual care includes 1) variable provider counseling with limited or variable EHR notifications or counseling support; 2) no distribution of print medication information materials, including FDA Medication Guides in clinics and variable distribution in pharmacies; and 3) limited or no active surveillance of medication use postvisits.

Intervention: EMC² **Strategy.** The final, vetted version of the EMC² intervention from Phase I will be imparted. In brief, there are several components to this strategy that will be embedded into the workflow via EHR/patient portal platforms, mostly automating their implementation. Following patient movement through a provider visit, the following activities will occur for a select list of pre-specified medications:

- 1) Prescribers will receive a 'Best Practices Alert' which recommends patient counseling on medication use and provides an overview of key medication risks
- 2) Patients will receive a Medication Guide + Summary with their After Visit Summary
- 3) Patients will be asked to complete a brief questionnaire on medication use via the patient portal post visit (at both 1 week and 1 month post visit for this phase of the study)
- 4) Portal assessment results and feedback will be provided to the clinic via an inbox message. Clinic staff will respond to any identified problems according to their own clinical care protocols.

Number of Patients:

While our expected sample size for this pragmatic study is 300, we will recruit 330 patients (~200 at NU, ~100 at ACCESS; we anticipate 90% retention among the recruited sample by 3 months (n=297). We therefore will oversample to accommodate some attrition.

Statistical Analysis:

We will perform analyses to address each of the aims using SAS v9.4 (SAS Institute, Cary, NC). The proposed trial uses a cluster-randomized design where the prescribing physician will be randomized to one of two arms (usual care, EMC²). Given the brief follow-up period, we anticipate ~90% retention at T2 interview. These estimates result in 330 patients recruited with an anticipated 300 patients (150 per arm, 6 per physician) available for primary data analysis.

We will use generalized linear mixed models (GLMM) to test treatment effects, specifying identity link for continuous and the logit link for binary outcomes using PROC GLIMMIX in SAS (v.9.4). All tests of treatment effects will be conducted at a 2-sided alpha level of 0.05.

Resources Available:

This study is led by senior health services researchers with expertise in chronic disease management, health literacy, and complex research designs. Additionally, the project staff have worked on similar research projects and have adequate training to carry out the proposed pragmatic study.

Setting:

This study is being conducted with patients from clinics within Northwestern Medical Healthcare (NMHC) and Access Community Health Network (ACCESS). All physicians within the practice will be informed of the study. All telephone interviews will take place in a private space at all study sites.

2. Schedule of Activities

Table 1 shows study timeline.

Visit						
Days from Initial Index Visit	1-2	3-14	15-21	21-28	29-36	90-104
Pragmatic Study Procedure						
Screening Phone Call	X					
Written Informed consent	X					
T1 In Person* Interview	X	X				
Patient sent email to complete portal		X		X		
questionnaire (expires after 2 weeks)						
If questionnaire not complete reminder			X		X	
email sent (sent two days after initial email						
to complete portal questionnaire)						
T2 Phone Interview						X

^{*}T1 interview may be completed over the phone if an in-person interview cannot be conducted.

3. Introduction

3.1. Pragmatic Study Rationale

Research has repeatedly demonstrated that individuals lack essential information on how to safely take prescribed (Rx) medications(1-4). An Rx communication and adherence strategy may be helpful for prescribers to ensure that patients are adequately informed about the medications they are taking and activated to sustain safe, appropriate use. We are therefore proposing to refine and evaluate our EMC² strategy to support safe prescription medication use.

3.2. Background

Inadequate patient knowledge has been cited as a root cause of unintentional misuse and non-adherence, which can lead to suboptimal treatment benefits and/or serious adverse drug events(5, 6). But this should not be surprising, as neither physicians nor pharmacists routinely counsel patients on their medication regimens(5, 7, 8). Instead, patients heavily depend on product labeling, such as package inserts, container labels, leaflets, and Medication Guides and/or Medication Summaries— all of which are limited in their clarity and effectiveness (5, 9, 10). Our team has found that even when evidence-based, health literacy best practices are employed to these written tools, the elderly and those with low literacy continue to be inadequately informed and are therefore at greater risk for medication errors and unintentional non-adherence(9).

An Rx communication and adherence strategy may be helpful for prescribers to ensure that patients are adequately informed about the medications they are taking and activated to sustain safe, appropriate use. This is most salient for Rx regimens the Food & Drug Administration (FDA) has deemed to possess serious public health concerns, warranting additional risk minimization activities beyond the product label [including a Risk Evaluation and Mitigation Strategy (REMS)]. To our knowledge, no such strategy exists to support and monitor outpatient medication use in a cost-sustainable manner.

A pilot study was recently conducted to assess the feasibility and acceptability of an Electronic health record-based Medication Complete Communication (EMC²) strategy that leverages electronic health record (EHR) technologies to: 1) prompt and guide provider counseling using 'best practice alerts (BPAs); 2) automate the delivery of Medication Guides and/or plain language Medication Summaries (Medsheets) at prescribing; 3) activate patients post-visit via the patient portal to confirm they have sufficient Rx information and are taking their Rx regimens properly; and 4) engage the clinical team to help patients overcome any barriers to adherence or safety. The results of this pilot were positive; the EMC² strategy was successfully implemented at two diverse, academic clinic practices utilizing the EPIC EHR. Findings include:

- ≥80% threshold for success achieved for BPAs, Med Guide/Medsheet delivery;
- While the Portal Survey was able to be consistently sent out to patients, this was most reliable among patients who already had an active Epic MyChart account;
- Results indicate high levels of patient satisfaction with EMC² tools and substantially higher rates of providerpatient counseling than reported previously in the scientific literature

Key lessons learned from the pilot were then used to inform this pragmatic trial to evaluate the efficacy of the EMC² intervention, specific to its ability to improve counseling rates, patient understanding and safe use of select medications compared to usual care.

3.3. Benefit/Risk Assessment

Risk to Patients:

Participation in the study poses minimal risk of psychological, social or economic harm. Informing patients in advance that they may decline to answer any questions asked during the interview will mitigate any risks associated with expressing their opinions (e.g., feeling uncomfortable). They will also be assured they can terminate their participation in the study at any time without penalty. The risk/benefit ratio is low. Minimal to no risk is expected for patients in this study.

Potential Benefits to Patients:

It is possible that patients enrolled in the intervention study arms may directly benefit in that they may have, as a result of this study, a better functional understanding of their medication. The results of this study may provide

important information regarding how strategies can be implemented via the EHR and computer technologies to support safe and appropriate medication use.

Provisions to Protect the Privacy Interests of Patients:

In order to preserve patients' confidentiality rights, research patients will be assigned code numbers that will be used to identify all the information collected. Using these codes, none of the collection forms will contain the names of the patients. All electronic data will be stored on a password-protected computer. A master study tracking database via Microsoft Access, at Northwestern, will contain information linking patients to their study identification numbers. This database will be encrypted and password protected and/or, kept on a secure server, and only accessible by Northwestern study personnel. ACCESS participants will be additionally tracked in their EPIC EMR system, only accessible by ACCESS study personnel. Survey data will be stored in a REDCap. The data will not contain any identifiable information. Individual study identification numbers will be assigned to each patient and only this number will appear on the survey.

All enrolled patients will provide written consent, include HIPAA authorization, for the collection of all data. Only authorized personnel listed on the IRB and approved by the PI will have access to the data.

4. Objectives and Endpoints

Table 2 shows the objectives and endpoints of the pragmatic study.

Table.2.

Objectives	Endpoints				
Primary • Test the effectiveness of the EMC ² Strategy, compared to usual care on improvement in patient knowledge of prescribed medications	Medication-specific knowledge measured by demonstrated proper understanding of indication, risks and benefits, and side effects at 3 months.				
Secondary • Test the effectiveness of the EMC ² Strategy, compared to usual care on improvement in safe use and adherence to prescribed medications	Medication adherence measured by fill, time to fill, demonstrated proper use, and the ASK-12. at 3 months				
Tertiary/Exploratory • Evaluate the fidelity of the EMC ² Strategy	 Patient report of provider counseling Patient report of receipt of print Rx information Completion of EHR portal survey Clinic follow-up (yes or no) for patients identifying Rx concerns via portal survey 				

Abbreviations: EMC²- Electronic health Record-based Medication Complete Communication

5. Pragmatic Study Design

5.1. Overall Design

For Phase II, we will conduct a 2-arm, multi-site, physician-randomized pragmatic trial to evaluate the impact and scalability of a refined version of the Phase I, finalized EMC² strategy to promote actual safe medication use. There will be two study arms: the EMC² Strategy, as refined from findings in Phase I, or usual care. Prescribers will be randomized to study arm prior to the initiation of the study. As patients are enrolled in the study, they will be assigned to either intervention or usual care arms based upon the assignment of their physician (see 7.3 Method of Treatment Assignment). We will follow patients for up to three months after receiving a new prescription or a dose change (refills allowed at ACCESS sites only) to determine whether those receiving the EMC² Strategy are more knowledgeable, more likely to be safely using their medication, and more adherent (as measured by fill (yes or no), time to fill (days from prescription order to pharmacy pick-up), self-reported behavior, and demonstrated use). We have powered this study as a randomized trial to detect meaningful effects of our intervention. As such, findings will support the more widespread EMC² adoption and dissemination.

Multi-Site Research:

The performance sites include Northwestern University, Northwestern Medical Group, and Access Community Health Network. All sites will be involved in the development of EHR tools. Northwestern University will be the data management site and Northwestern RAs will conduct all data collection.

All required approvals will be obtained at each site prior to project implementation. In addition:

- a. Once IRB approval is obtained at Northwestern University for study materials and protocol, Access Community Health Network will be sent approved materials via email. Northwestern will send any modifications made to be approved prior to implementation. All study sites will have regular conference telephone calls during both phases of the study to discuss any problems and interim results, and to discuss any possible changes that need to be made to study materials and protocol.
- b. All non-compliance with the study protocol or applicable requirements will be reported in accordance with local policy.

Study-Wide Recruitment Methods:

Patient Recruitment Process:

At all study sites, a research coordinator (RC) will log in to EPIC to look for an alert if a patient received a new prescription or a dose change for one of the study medications at the study clinic. However, we anticipate that mostly patients with a new prescription will be recruited due to the design of the intervention within EPIC. Alerts in EPIC will only be activated for patients that have not opted out of research. RC will then review the EHR to confirm new or changed prescription and patient portal status. Recruitment will be done by the RC via telephone. Patients will be called via telephone within 1-14 days after their index clinic visit. If they are interested in participating or learning more about the study, the RC will obtain verbal permission to ask the patient a brief series of questions to determine eligibility. If eligible, the RC will schedule a time to complete the T1 interview in person and obtain written consent. If an in person interview is not able to be completed due to COVID-19 institutional policy, the RC will schedule a time to complete the T1 interview over the phone. If all T1 questions cannot be completed in person, they will be completed over the phone.

Table 3 shows patient payment.

Patient Payment:

Research Interview	Payment	Form of Payment
		Cash at close of interview for in person interview OR
T1	\$ 30	Money Order or PNC Visa gift card for telephone interview

T2 S 40 Money order or PNC Visa Gift Card of interview	d sent at close
--	-----------------

Research Coordinator Training. The project lead will lead sessions to orient the research staff to the surveys and study protocols (e.g., interview process, use of laptop PCs, data security). All interviewers will be required to demonstrate competence in survey administration. All RCs have completed human subjects training (CITI) and intensive training from Drs. [name] and [name] in interview protocols and safe data transfer.

Clinic Orientation. Within 1-2 weeks to the launch of the EMC² Strategy at the clinic, Drs. [name], [name], and/or [name] for Northwestern OR [name] for ACCESS Community Health Network will describe the study and what to expect over the upcoming several months to clinic providers and staff. Additional meetings may be held with staff responsible for following up with patients. We anticipate little orientation will be needed as most these sites participated in Phase I.

Study Timelines:

An individual patient will be involved in the study for a total of up to 3 months. They will complete a screener enrollment interview, a T1 in person or phone interview as soon as possible following the screener, and a final T2 interview on the phone at 3 months.

[figure not shown]
We anticipate that patient enrollment will actively take place until Q2, 2020.

Our proposed/anticipated study timeline is below.

Table 4 shows study measures and outcomes.

			Inter	view			
Variable	Instrument(s) or Measure(s)		T1			T2	EHR Reviev
Covariates		_					
Socio-demographics	Age, sex, race/ethnicity, education, income, insurance/work status, living situation	Summary	•				
Baseline Health Status	Self-reported overall health/chronic conditions	ung	•				
Health Literacy	Chew		•				
Social Support	Tangible social support scale, marital status	Med	•	Week	month		
Patient Activation	Consumer Health Activation Index (CHAI)		•	Ve.	0		
Effectiveness Outcomes		and		7	Е		
Medication Knowledge	Dosage, storage, indication, risks and benefits, side-effects		•		Ξ	•	
Medication Adherence	Self report fill and time to fill	ing	•	ij	ire	•	
	Proper use	sel	•	Ĕ	na	•	
	ASK-12	Ë	•	ō	ou	•	
Fidelity Outcomes		counseling,		Questionnaire-	Questionnaire		
Provider Counseling	Receipt of provider counseling (yes/no)		•	ne	ne		
Qualify of Provider Counseling	CAHPS- communication about medicines	RX	•	g			
Receipt of Materials	Receipt of Med Guide (yes/no)	Ă,	•	rta	tal		
Perceived Helpfulness	How helpful was intervention? (1 to 10 scale)	BPA,	•	Portal	Portal		
Pharmacy Counseling	Receipt of pharmacy counseling (yes/no)		•	-	а.	•*	
Qualify of Pharmacy Counseling	CAHPS- communication about medicines	Visit-	•	1		•*	
Receipt of Portal Email	Completion of portal assessment (yes/no)					•	
	How helpful was intervention? (1 to 10 scale)	Clinic				•	
Clinic Staff Follow-Up Counseling	Receipt of counseling (yes/no)	C				•	
Quality of Clinic Staff Counseling	Self-reported clinic follow-up					•	
Frequency of Clinic Follow-Up	EHR Review of clinic contact with patient			1			•

Figure.1 Illustrates the study design

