6.2. Exclusion Criteria

Patients will be excluded from study enrollment if they meet any of the following criteria at screening/enrollment:

- 1) Severe, uncorrectable vision
- 2) Severe hearing impairments
- 3) Severe cognitive impairment
- 4) No access to the internet or patient portal account

Adults unable to consent, individuals under the age of 18, and prisoners will be excluded from this research.

For many patient characteristics, we will be able to ascertain differences between those participating and those who refuse to be included in the study, to determine potential bias. Additionally, research teams at both sites will limit recruitment of patients prescribed Metformin to 50 patients per site and will only recruit those with a new prescription. This quota has been set in place to ensure adequate representation of other study drugs with less volume compared to Metformin.

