7.1. Treatments Administered

This pragmatic study involves a comparison of intervention administered with standard of care in routine care.

Study Arms.

Usual Care: For this study, current usual care includes 1) variable provider counseling without any EHR notifications or counseling support; 2) variable distribution of print medication information materials, including FDA Medication Guides in clinics and variable distribution in pharmacies; and 3) limited or variable active surveillance of medication use post-visits.

Intervention: EMC² Strategy: There are several components that will be embedded into the workflow via EHR/patient portal platforms, mostly automating their implementation. Following patient movement through a provider visit, the following 6 activities will occur:

- 1. *Physician Medication Alert:* If a prescribing physician attempts to place a new order or change to an existing study medication prescription, an EHR-generated alert will notify the provider that the medication requires patient counseling. Physicians can opt to ignore this alert.
- 2. *Provider Counseling Support:* Content from the 1-page, Med Guide Summary will appear on the screen, if selected by the provider, to orient and inform provider-patient discussion.
- 3. Automated Delivery of Med Guide + Summary: When patients leave an encounter, the medication order in Epic will automatically cue printing of both the 1-page, health literate Med Guide Summary for study medications and a full Med Guide, if applicable (latter is required by FDA for certain medications only, the former designed to enhance comprehension). If the medication was ordered during a telemedicine encounter, the Med Guide Summary will automatically populate in the patient portal.
- 4. Follow-Up Portal Questionnaire: Within 1 week post-visit, patients will receive an automated email prompting them to log on to the patient portal. Patients' will be asked to fill out a short set of questions related to medication adherence, and other medication-related concerns (i.e. cost, side effects). If patients have not completed the questionnaire within 2 days, another email reminder will be sent. The information submitted back by the patient will be stored in the EHR.

Content in question form and corresponding responses for the portal questionnaire will be revised from prior evaluation scripts and written by Drs. [name], [name], [name], and [name].

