7.4. Blinding

This is an open-label pragmatic study. As with most behavioral interventions, it will not be possible to fully blind researchers, healthcare providers, and study patients to intervention vs. usual care assignments. However, we have purposefully designed our trial to prevent certain threats to contamination between study arms. Patients will be told they will receive one of two models of care. While they will not be deliberately made aware of the approach not received, we do recognize that there is an unavoidable risk of patients learning from other patients involved in the study.

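### Patients are found and recruited after prescribers are randomised, through an alert not shown to run alike in both arms, leaving the primary comparison open to recruitment bias of unknown size

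*Combined protocol and SAP*

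**What the plan says.** Sections 5.1 and 7.3 randomise prescribers before the study begins, and each patient takes the arm of the prescriber. Section 5.1 (Patient Recruitment Process) has a coordinator at every site "look for an alert if a patient received a new prescription or a dose change". It expects that "mostly patients with a new prescription will be recruited due to the design of the intervention within EPIC", and says alerts are active only for patients who have not opted out of research. The next step is: "RC will then review the EHR to confirm new or changed prescription and patient portal status. Recruitment will be done by the RC via telephone". The coordinator screens for eligibility, schedules the T1 interview and obtains consent.

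In Section 7.1 the first intervention component is that "an EHR-generated alert will notify the provider that the medication requires patient counseling". The same section describes usual care as "variable provider counseling without any EHR notifications or counseling support". The Synopsis instead allows usual care limited or variable notifications. Section 6.1 counts recruitment volume at ACCESS in best practice alerts, 60% of which were ineligible, mainly because they were refills.

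Section 7.4 states that "it will not be possible to fully blind researchers, healthcare providers, and study patients". Section 6.2 says that for many characteristics "we will be able to ascertain differences between those participating and those who refuse". Section 10.3.2.1 promises a description of patient disposition. Section 10.3.2.2 compares T1 characteristics by arm and adjusts for those with p < .05. Section 10.3.3.1 adds potential confounders to the primary model.

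**The concern.** When clusters are randomised first and individuals recruited later, randomisation balances the prescribers but not the patients who end up in the data. If patients in the two arms are found, approached, judged eligible or persuaded at different rates, the arms hold different kinds of patient. A difference in medication knowledge at T2 may then reflect who was recruited rather than what EMC² did, and a real effect may equally be hidden.

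Section 5.4 gives good reasons for randomising physicians and for not randomising patients before the visit, so recruitment after randomisation is unavoidable here. What the plan leaves open is whether recruitment works the same way in both arms. The alert used to find patients resembles the first component of the intervention, and the plan describes no equivalent for usual care. By the time of the call, intervention patients have already been through a visit at which they should have been given the Summary.

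**Working it through.** **Step 1. Does the same alert run in both arms?**

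| Text | Points to |
|---|---|
| 5.1: case finding by alert, at all sites | a tool meant to cover both arms |
| 5.1: alert limited to patients not opted out of research | a recruitment flag, possibly silent |
| 5.1: recruitment mix follows the EPIC intervention build | the intervention alert |
| 6.1: recruitment volume counted in best practice alerts | the intervention alert |
| 7.1: usual care has no EHR notifications | no alert for usual-care prescribers |
| Synopsis: limited or variable notifications in usual care | some alerts in usual care |

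These cannot be settled from the text. No section describes a silent alert or order report for usual-care prescribers.

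**Step 2. Is the arm hidden from those who recruit?** Section 7.4 says only that full blinding is not possible. No section masks coordinators or requires patients to be approached consecutively. Section 10.3.1 reveals provider identities after randomisation, without saying to whom. Section 10.3.3.3 puts extra questions to intervention patients about the Summary and its helpfulness, and Table 4 places such items at T1. Whoever conducts T1 must therefore know the arm by that point.

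**Step 3. What precedes the call?** Section 5.1 allows calls 1-14 days after the visit (Section 6 says within 7 days; Table 1 shows days 1-2). Section 7.1 delivers the Summary as the patient leaves the encounter, or through the portal after telemedicine, and sends a portal email within a week (days 3-14 in Table 1). Having a portal account is an inclusion criterion (6.1), and the coordinator's check to "confirm new or changed prescription and patient portal status" can fall in the same window.

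**Step 4. Scale.** Inputs from Section 10.1: SD 28.4, 150 per arm, 6 per provider, ICC 0.001, two-sided alpha 0.05, power 80%. Section 7.3 gives about 50 prescribers, hence 48 df.

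SE = 28.4 × √[(2/150) × (1 + 5 × 0.001)] = 3.288.

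Detectable difference = (2.011 + 0.849) × 3.288 = 9.40. At ICC 0.01, SE = 3.360 and the result is 9.61. Both match the plan's 9.4 and 9.6, so no sample-size figure is in dispute.

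Now let recruitment shift the arm difference by b points. The values of b are assumptions. With a noncentral t on 48 df and noncentrality b/3.288 for type I error, or (9.4 − b)/3.288 for power when b runs against EMC²:

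| b (assumed) | Type I error | Power at a true 9.4 |
|---|---|---|
| 0 | 5.0% | 80% |
| 1 | 6.0% | 71% |
| 2 | 9.2% | 60% |
| 3 | 14.6% | 48% |
| 4 | 22.2% | 36% |
| 5 | 32.0% | 26% |

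A bias of 2 would arise if the arms differed by 20 percentage points in the share of a patient type scoring 10 points higher (0.20 × 10 = 2).

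**Step 5. Differential willingness.** Assume 40% participation in one arm and 60% in the other, and a correlation r of 0.1-0.3 between willingness and knowledge. Shift = r × 28.4 × (0.386/0.4 − 0.386/0.6) = r × 28.4 × 0.322, or 0.9 to 2.7 points (10-29% of 9.4). This is before any covariate adjustment.

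**The case against.** The strongest reply is that the text fits a sound procedure. The notifications denied to usual care in Section 7.1 are those that support the provider's counselling, whereas Section 5.1 describes something a coordinator logs in to see at all sites, filtered on research opt-out. A silent flag in both arms would fit. If no usual-care patient could trigger it, this route could not yield the planned 150 per arm. This stands: a reader might infer that usual-care patients have no means of being found, and the documents do not support that. They leave the point unsettled.

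A reader might also infer that coordinators know the arm when they call and pick whom to phone. Neither is stated. Section 5.1 says patients will be called, most eligibility criteria are factual, and the metformin cap in Section 6.2 is per site, not by arm. What remains is that nothing hides the arm and nothing requires consecutive approach.

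Third, the plan has safeguards: stratified randomisation, the disposition report, the refuser comparison, and covariate adjustment. They help only in part. The refuser comparison is not stated to be by arm, and it omits anyone who never triggered an alert or was never called. T1 follows the visit, so demographic covariates are safe, but measures such as activation may already reflect exposure.

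Finally, masking will be weak. Coordinators open a chart tied to the prescriber, and the prescriber determines the arm. This stands as well, and it limits what the fix can achieve.

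**Conclusion.** The point holds as an exposure to bias, not as demonstrated bias. Patients are identified, screened and consented after allocation; the documents do not show that the case-finding alert runs identically in both arms; and they describe neither masking of coordinators nor consecutive approach. Portal eligibility is checked at a time when the intervention could have influenced it, although no section reports that patients opened accounts for that reason.

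The size is unknown. The type I error range of 6% to 32% rests on assumed biases of 1 to 5 points and shows sensitivity only. A reader might take the 0.9-2.7 point illustration as the gain from masking coordinators. It is not: it models unequal patient willingness, which can arise from exposure before the call and which masking the recruiter would not remove.

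The change should be made because it is cheap and alters no endpoint, model or sample size: recruitment stays at 330, evaluable patients at 300 and the detectable difference at 9.4.

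**What to change.** - In Section 5.1, identify patients in both arms from the same order-based EPIC report or the same silent trigger, keep the research opt-out filter, and approach patients consecutively. Define qualifying orders identically by arm, including the refills allowed at ACCESS.
- Leave the arm off the coordinators' work list.
- Assess portal-account status as of the order date.
- Ask intervention-specific probes after the outcome questions at both T1 and T2.
- Report, by arm, the numbers of orders, eligible, called, reached and consented, and compare participants with refusers by arm.
- Reconcile the descriptions of usual-care notifications in the Synopsis and Section 7.1.

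The cost is a small change to an EHR report, a reordered interview and one flow table; the documents give no figure for staff time. Masking will be imperfect because the chart is opened. Differential consent among patients already exposed would remain, but the by-arm flow would let readers judge whether it occurred. The refill provision in Section 6.1 suggests that recruitment may be under way. If so, the flow table and order-date portal status could still be extracted, assuming the EHR retains those dates.
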